8.3.3 Follow-Up of Adverse Events and Serious Adverse Events

After the initial adverse event or serious adverse event report, the investigator is required to proactively follow each patient at subsequent visits or contacts. All adverse events will be followed until the event has resolved to baseline grade or better, or the event is assessed as stable by the investigator, or the patient is lost to follow-up (as defined in Section 7.3), or the patient withdraws consent. Further information on follow-up procedures is provided in Appendix 2.

8.3.4 Regulatory Reporting Requirements for Serious Adverse Events

Prompt notification (i.e., within 24 hours of awareness) by the investigator to the Sponsor of a serious adverse event is essential so that legal obligations and ethical responsibilities towards the safety of patients and the safety of a study treatment under clinical investigation are met.

The Sponsor has a legal responsibility to notify both the local regulatory authority and other regulatory authorities about the safety of a study treatment under clinical investigation. The Sponsor will comply with country-specific regulatory requirements relating to safety reporting to the regulatory authority, Institutional Review Boards or Ethics Committees (IRBs/ECs), and investigators.

For all studies except those utilizing medical devices, investigator safety reports must be prepared for suspected unexpected serious adverse reactions according to local regulatory requirements and Sponsor policy and forwarded to investigators as necessary.

To determine reporting requirements for serious adverse event cases, the Sponsor will assess the expectedness of these events through use of the reference safety information in the document listed below:

Drug	Document
Faricimab	Faricimab Investigator's Brochure

The Sponsor will compare the severity of each event and the cumulative event frequency reported for the study with the severity and frequency reported in the applicable reference document.

Reporting requirements will also be based on the investigator's assessment of causality and seriousness, with allowance for upgrading by the Sponsor as needed.

An investigator who receives an investigator safety report describing a serious adverse event or other specific safety information (e.g., summary or listing of serious adverse events) from the Sponsor will review and then file it along with the Investigator's Brochure and will notify the IRB/EC, if appropriate according to local requirements.

8.3.5 Pregnancy

Female patients of childbearing potential will be instructed through the Informed Consent Form to immediately inform the investigator if they become pregnant during the study or within 3 months after the final dose of faricimab.

If a pregnancy is reported, the investigator should inform the Sponsor within 24 hours of learning of the pregnancy and should follow the procedures outlined in Appendix 4.

All pregnancies reported during the study should be followed until pregnancy outcome, with follow-up information on the infant collected according to procedures outlined in Appendix 4. The Sponsor or a designee may follow up by telephone, fax, email, and/or a monitoring visit to obtain additional case details and outcome information (e.g., from hospital discharge summaries, consultant reports, autopsy reports) in order to perform an independent medical assessment of the reported case.

Abnormal pregnancy outcomes (e.g., spontaneous abortion, fetal death, stillbirth, congenital anomalies, ectopic pregnancy) are considered serious adverse events.

8.3.6 Cardiovascular and Death Events

Information on reporting deaths is provided in Appendix 2.

8.3.7 Anticipated Events Not Qualifying for Expedited Reporting

Events not qualifying for expedited reporting will not be defined for this study.

8.3.8 Adverse Events of Special Interest

Adverse events of special interest are required to be reported by the investigator to the Sponsor immediately (i.e., no more than 24 hours after the investigator becomes aware of the event; see Section A_{2-5} for reporting instructions). Adverse events of special interest for this study are as follows:

- Cases of potential drug-induced liver injury that include an elevated ALT or AST in combination with either an elevated bilirubin or clinical jaundice, as defined by Hy's Law (see Section A2–7.6)
- Suspected transmission of an infectious agent by a study treatment, as defined below:

Any organism, virus, or infectious particle (e.g., prion protein transmitting transmissible spongiform encephalopathy), pathogenic or non-pathogenic, is considered an infectious agent. A transmission of an infectious agent may be suspected from clinical symptoms or laboratory findings that indicate an infection in a patient exposed to a medicinal product. This term applies only when a contamination of the study treatment is suspected.

- Sight-threatening adverse events: An adverse event is considered to be sightthreatening and should be reported expeditiously if it meets one or more of the following criteria:
 - It causes a decrease of ≥ 30 letters in visual acuity (VA) score using Early Treatment Diabetic Retinopathy Study (ETDRS) or greater than 0.6 using LogMAR or more than 6 lines using Snellen (compared with the last assessment of VA prior to the most recent assessment) lasting more than 1 hour.
 - It requires surgical or medical intervention (i.e., conventional surgery, vitrectomy, vitreous tap, or biopsy with IVT injection of anti-infective treatments, or laser or retinal cryopexy with gas or a medication) to prevent permanent loss of sight.
 - It is associated with severe intraocular inflammation (i.e., endophthalmitis, 4+ anterior chamber cell/flare, or 4+ vitritis; see Section A2-7 and Appendix 7 for intraocular inflammation terms and definitions).

All of the above-listed sight-threatening adverse events should be reported as serious adverse events, listing the underlying cause (if known) of the event as the primary event term.

Descriptions of risks and management of the above-listed adverse events are provided in Appendix 3

8.3.9 Device Product Complaints (Including Failures and Malfunctions)

In this study, 6-mg faricimab single-use PFS with co-packaged injection filter needle is considered a drug-device combination product. The biologic constituent part is

6-mg Faricimab Prefilled Syringe—F. Hoffmann-La Roche Ltd 30/Protocol GR43742, Version 1

faricimab. The device constituent parts are the prefilled syringe with the extended finger flange and the coupled plunger as well as and the injection filter needle. The investigator must report all medical device complaints (including failures and malfunctions) and any associated adverse events to the Sponsor, as described in Appendix 5 .

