5.2 EXCLUSION CRITERIA

5.2.1 Exclusion Criteria for Patients

Patients are excluded from the study if any of the following criteria apply:

• Pregnancy or breastfeeding, or intention to become pregnant during the study or within 3 months after the final dose of faricimab

Female patients of childbearing potential must have a negative urine pregnancy test result during screening and on Day 1.

- Requirement on Day 1 for continuous use of any medications and treatments indicated in Section 6.8.2, Prohibited Therapy
- Participation in an investigational trial that involves treatment with any drug or device (with the exception of vitamins and minerals) within 3 months prior to Day 1
- Stroke (cerebral vascular accident) or myocardial infarction within 6 months prior to Day 1
- History of a severe allergic reaction or anaphylactic reaction to a biologic agent or known hypersensitivity to any component of the faricimab PFS injection, studyrelated procedure preparations, or any of the anesthetic and antimicrobial preparations used by a participant during the study
- History of other disease, metabolic dysfunction, physical examination finding, or clinical laboratory finding giving reasonable suspicion of a condition that

6-mg Faricimab Prefilled Syringe—F. Hoffmann-La Roche Ltd 18/Protocol GR43742, Version 1 contraindicates the use of faricimab or renders the patient at high risk for treatment complications in the opinion of the investigator

- Uncontrolled hypertension (systolic blood pressure >180 mmHg and/or diastolic blood pressure >100 mmHg while a patient is at rest)
- Systemic treatment for suspected or active systemic infection on Day 1
- Patients legally blind in the study eye on Day 1 (legal blindness: Best-corrected visual acuity [BCVA] of 20/200 or less).
- History of or any current clinically relevant intraocular inflammation or ocular inflammatory reaction (any grading from trace and greater is excluded), including non-infectious uveitis or infectious uveitis, or sterile inflammatory reaction after previous IVT injections with any agent in either eye
- Suspected or active ocular or periocular infection in either eye on Day 1
- History of or any current indication of excessive bleeding and recurrent hemorrhages, including any prior excessive intraocular or subconjunctival bleeding or hemorrhages after IVT injection or intraocular procedures in either eye
- Uncontrolled glaucoma in the study eye

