Appendix 8 Refraction and Best-Corrected Visual Acuity Testing

SCOPE

Refraction and best-corrected visual acuity (BCVA) assessment must be conducted before pupil dilation. BCVA data for study eyes should be entered in appropriate eCRF log.

BCVA may be assessed on any standard visual acuity (VA) chart according to local practice. The Early Treatment Diabetic Retinopathy Study (ETDRS) chart is recommended, but Snellen and LogMAR are also acceptable.

Note: the chart used to measure a participant's VA on Day 1 must remain consistent for the duration of the patient's participation in this study.

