Appendix 9 Unscheduled Safety Assessment Visit

Assessments ^a		
Mandatory assessments:		
Best-corrected visual acuity ^{b, c}		
Slitlamp examination		
Dilated binocular indirect high-magnification ophthalmoscopy		
Intraocular pressure ^c		
Adverse events ^d		
Assessments at the discretion of the Investigator ^e :		
Concurrent ocular procedures		
Concomitant medications		
Hematology, serum chemistry panel, and coagulation as deemed appropriate by the investigator		
Ocular imaging, as necessary		
^a Participants will be instructed to contact the investigator at any time if they have		

- ^a Participants will be instructed to contact the investigator at any time if they have any health related concerns. If warranted, Investigators may ask the participant to return to the clinic for an unscheduled safety assessment visit during the study period. Best-corrected visual acuity (BCVA), slitlamp, intraocular pressure (IOP), and indirect ophthalmoscopy examinations must be conducted at unscheduled safety visits. All other assessments are at the discretion of the investigator. It is recommended to perform ocular assessments on both eyes.
- ^b Perform finger -counting test followed by hand motion and light perception tests when necessary. BCVA should assessed at a 4-meter starting distance when using Early Treatment Diabetic Retinopathy Study (ETDRS) chart or equivalent starting distance per local practice guidelines if using Snellen or LogMAR.
- ^c The method used for the BCVA and intraocular pressure measurement for a participant must remain consistent throughout the study.
- ^d Adverse event causality to be evaluated by an ophthalmologist.
- If additional assessments (at the discretion of the Investigator) are performed per standard of care, please add the following information to the adverse event additional case details field: describe the assessments performed (e.g., inflammatory laboratory panel, SD-OCT, etc.) and describe any relevant findings that could help contextualize the adverse event.

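### The Snellen limit of more than 6 lines in Section 8.3.8 is not equivalent to the ETDRS and LogMAR limits beside it, and off-chart vision results have no place on any of the three scales

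*Protocol*

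**What the plan says.** Section 8.3.8 lists three alternative criteria for a sight-threatening event, any one of which is enough. The first is a fall in visual acuity (VA) from the preceding assessment that lasts more than 1 hour. For ETDRS the limit is 30 letters or more. For the other charts it is "or greater than 0.6 using LogMAR or more than 6 lines using Snellen". An event that qualifies is reported to the sponsor within 24 hours and as a serious adverse event (SAE).

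Appendix 8 allows any standard chart: the ETDRS "chart is recommended, but Snellen and LogMAR are also acceptable". Appendix 8 and footnote c of Appendix 9 then require the same chart and method for a patient throughout. No section gives a Snellen line layout or the lowest line of any chart. Appendix 9 gives a starting distance of 4 meters for ETDRS and leaves the equivalent for Snellen and LogMAR to local practice.

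Section 5.2.1 excludes legally blind study eyes, with the definition "legal blindness: Best-corrected visual acuity [BCVA] of 20/200 or less". Any study eye better than 20/200 may therefore enter.

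Section 8.2.1 calls for finger counting within about 15 minutes of the injection, with hand-motion and light-perception tests if needed. At unscheduled safety visits, footnote b of Appendix 9 asks for finger counting "followed by hand motion and light perception tests when necessary". Section 8.3.8 mentions none of these results.

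**The concern.** The first criterion should classify the same loss of vision in the same way whichever permitted chart a site uses. A count of Snellen lines does this only if each line is worth the same amount. On charts with wide steps at the poor end, a large loss can cover few lines. A patient measured on Snellen could then have a loss well above 0.6 LogMAR that does not meet the written limit, while the same loss on ETDRS or LogMAR would.

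There is a second gap. When vision falls below the chart, the protocol orders tests whose results cannot be turned into letters, LogMAR units or lines. The criterion then gives no answer, and it does so for the largest losses.

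At stake is whether an event is an AESI, and so an SAE under the protocol's own rule, with 24-hour reporting. Section 9.2 gives safety evaluation as the purpose behind the sample size. With about 35 patients, a single event is 1/35, or about 3%.

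**Working it through.** **Inputs from the protocol.** Limits: at least 30 letters, more than 0.6 LogMAR, more than 6 lines (8.3.8). Entry: study eye better than 20/200 (5.2.1).

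**Assumed inputs.** Snellen layouts and chart floors, which the protocol does not give; a range is shown.

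**1. The protocol's own equivalence.** 0.6/30 = 0.02 LogMAR per letter; 30/6 = 5 letters per line; 0.6/6 = 0.1 LogMAR per line. The three limits agree in size if every line is a 0.1 step. (ETDRS is inclusive and the other two are strict; that boundary difference is a separate matter.)

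**2. Uneven Snellen chart ending at 20/200.** Assumed lines: 20-25-30-40-50-70-100-200. Loss in LogMAR = log10(200/baseline denominator); letter equivalent = LogMAR/0.02. More than 6 lines means at least 7.

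| Baseline | Lines down to 20/200 | LogMAR loss | Letters | More than 6 lines? | More than 0.6 LogMAR? |
|---|---|---|---|---|---|
| 20/20 | 7 | 1.00 | 50 | yes | yes |
| 20/25 | 6 | 0.90 | 45 | no | yes |
| 20/30 | 5 | 0.82 | 41 | no | yes |
| 20/40 | 4 | 0.70 | 35 | no | yes |
| 20/50 | 3 | 0.60 | 30 | no | boundary |
| 20/70 | 2 | 0.46 | 23 | no | no |
| 20/100 | 1 | 0.30 | 15 | no | no |

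For baselines of 20/25, 20/30 and 20/40 both readings are on the chart, the loss exceeds 0.6 LogMAR and 30 letters, and the Snellen rule is not met. This is a spacing problem. For 20/70 and 20/100 the chart ends before any scale reaches its limit; that is a floor problem, and converting units does not cure it.

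**3. Other assumed Snellen layouts: baselines that can lose more than 6 lines on the chart.**

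| Layout | Baseline needed |
|---|---|
| As above, with 20/400 added | 20/25 or better |
| As above, with 20/300 and 20/400 added | 20/30 or better |
| Even 0.1-LogMAR lines to 20/200 | 20/40 or better |
| Even 0.1-LogMAR lines to 20/400 | 20/80 or better |
| Even 0.1-LogMAR lines to 20/800 | every admitted eye |

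**4. LogMAR chart.** The limit is reachable on the chart only if baseline + 0.6 is below the chart floor.
- Floor 1.0 (20/200): baseline better than 0.4, about 20/50.
- Floor 1.3 (20/400): better than about 0.7, 20/100.
- Floor 1.6 (about 20/800): better than 1.0, so every admitted eye.

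**5. ETDRS.** Under the assumed conversion of letters = 85 − 50 × LogMAR, 20/160 (LogMAR 0.9) is 40 letters, and 40 − 30 = 10. The limit is reachable for every admitted eye if near-distance scoring down to 0 is used.

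**6. Off-chart results.** Sections 8.2.1 and 8.3.8 and Appendices 8 and 9, read together, assign no letter, LogMAR or line value to finger counting, hand motion or light perception. They also do not say whether falling off the chart meets the limit. This needs no assumption about charts.

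**The case against.** The strongest reply is that every Snellen figure above rests on a layout that the protocol does not give, and that the answer runs from only a 20/20 baseline to every admitted eye. That stands, and the size must be read as a range. It does not rescue the line count. The protocol permits any standard chart, so the limit should work on an unevenly spaced one, and nothing in the text rules such a chart out.

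A reader might infer that the LogMAR limit also runs off the chart. The documents do not support this in general. It happens only if the chart stops at about 20/200 to 20/400 with no closer testing. Appendix 9 speaks of a starting distance, which leaves room for a nearer one. ETDRS, the recommended chart, is unaffected if near-distance scoring is used.

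A reader might also infer that severe losses escape AESI reporting. They often would not. Intervention to prevent permanent loss of sight and severe intraocular inflammation each qualify alone under 8.3.8. The SAE definition in Appendix 2 covers persistent disability and important medical events. What remains is a loss lasting more than 1 hour, on an affected chart or off the chart, with neither of the other sight-threatening criteria met and classification left to judgement.

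Finally, a reader might infer that AESI counts will be biased and not comparable between sites. The protocol plans no patient safety endpoint, no hypothesis test and no comparison between sites, only description. Chart VA after the injection is taken only at unscheduled visits, so few patients could be affected. That inference should not be drawn.

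**Conclusion.** The point holds for the vision-change criterion in 8.3.8, and only there. Two defects remain.

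- **The Snellen line limit is not equivalent to the other two limits on an unevenly spaced chart.** On the assumed chart ending at 20/200, losses of 0.70 to 0.90 LogMAR, 35 to 45 letters, fail it. On even 0.1-LogMAR lines down to 20/800 no admitted eye is shut out.
- **Finger-counting, hand-motion and light-perception results have no value on any of the three scales.** This rests on the text alone.

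The number of events affected cannot be estimated from the protocol. No sample size or planned test is involved. The change is worth making because the limit is meant to apply by rule and the correction is small.

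**What to change.** In 8.3.8, replace the Snellen line count with conversion of the Snellen fraction to LogMAR, LogMAR = log10(denominator/20) for fractions written over 20, and apply the protocol's existing LogMAR limit. Add a conversion table to Appendix 8. The table should fix the rounding: 20/50 to 20/200 is log10(4) = 0.602 unrounded, which exceeds 0.6, but 0.6 when rounded to one decimal, which does not.

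Conversion cures uneven spacing, not the end of the chart. The sponsor should therefore also state how off-chart results count against the limit, for example through an assigned LogMAR value of its choosing. Making every fall to finger counting an automatic AESI is not proposed. It would set a new threshold, which an eye already near the bottom of its chart could meet with a small drop.

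The cost is about two sentences in 8.3.8 and one table in Appendix 8. No new assessment is needed. The downside is possibly a few more AESI reports.

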1.3 SCHEDULE OF ACTIVITIES

Table 1 Schedule of Activities for Health Care Providers

Health Care Providers				
	Screening	Preparation of Injection Observation	Injection Observation Period	Post-Procedure Interview ^a
Day(s)	-30 to 1	_3 to 1	1	1
Eligibility criteria	x			
IFU review phase		x		
HCP informed consent ^b		x		
Injection procedure and observation of HCP activities			x	
Post-procedure discussion ^a				x

HCP=health care provider; IFU=Instructions for Use.

^a After each patient procedure, HCPs will be reminded of the complaints procedure (see Appendix 5) to be followed in case any device failures or malfunctions were noted. Further discussion topics may be addressed, if deemed necessary by the human factors observers.

^b Pre-brief by human factors observers, with HCP informed consent signing (on the morning of Day 1 or afternoon of Day –1).

Patients				
	Screening ^a	Injection Procedure ^a	Safety Telephone Call	Safety Telephone Call
Day(s)	-30 to 1	1	3 (±1)	7 (±1)
Patient informed consent	x			
Review of inclusion and exclusion criteria	x	×		
Demographics	x			
Medical History	x			
Pregnancy test (urine)	x	x		
Baseline examination (BCVA ^b , slitlamp exam, indirect ophthalmoscopy)		x		
Injection administration		x		
Study eye predose IOP		x		
Study eye postdose IOP		x		
Finger-counting test °		x		
Adverse events		x	x	x
Concomitant medications	x	x	x	x

Table 2 Schedule of Activities for Patients

BCVA=best-corrected visual acuity; ETDRS=Early Treatment Diabetic Retinopathy Study; IOP=intraocular pressure; VA=visual acuity.

- ^a If screening and injection occur on the same day, assessments listed for both visits should be conducted only once before injection.
- ^b BCVA may be measured on any standard VA chart according to local clinical practice. Acceptable charts include ETDRS, Snellen and LogMAR. Refer to Appendix 8 for further details.

Note: in the event that a patient requires an unscheduled safety visit, the same method of VA assessment should be used as the baseline assessment.

^c Finger counting test will be performed in the study eye within 15 minutes of treatment.

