8.2 SAFETY ASSESSMENTS

8.2.1 Ocular Assessments

IOP will be measured in the study eye predose on Day 1.

Following study treatment, patients will remain at the clinic for approximately 30 minutes.

Finger-counting test followed by hand motion and light perception tests (when necessary) will be performed within approximately 15 minutes post-study treatment in the study eye.

IOP will be measured in the study eye after treatment. If there are no safety concerns following the study treatment, the participant will be allowed to leave the clinic. If the IOP value is of concern to the Investigator, the participant will remain in the clinic and be managed in accordance with the Investigator's clinical judgement. The same device must be used to measure pretreatment IOP and posttreatment IOP.

If applicable, the adverse event and the adverse event treatment (if applicable) will be reported on the appropriate eCRFs.

See Table 2 for the schedule of assessments performed during the study.

If warranted during the study duration (7 days), patients will be asked to return to the clinic as soon as possible for an unscheduled safety assessment visit (see Appendix 9).

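### The vision-loss criterion for sight-threatening events is inclusive on ETDRS but strict on LogMAR and Snellen, and it looks back only to the preceding acuity assessment

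*Protocol*

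**What the plan says.** Section 8.3.8 gives three routes by which an adverse event counts as sight-threatening. The first is a fall in visual acuity lasting more than one hour. On ETDRS the limit carries a greater-than-or-equal sign and is set at "30 letters in visual acuity (VA) score using Early Treatment Diabetic Retinopathy Study (ETDRS"). On the other charts the loss must be "greater than 0.6 using LogMAR or more than 6 lines using Snellen (compared with the last assessment of VA prior to the most recent" assessment). An event that meets any of the three routes is an AESI, is to be reported as an SAE, and must reach the sponsor within 24 hours.

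The chart is not fixed for the study. The footnotes to Table 2 (Section 1.3) say "BCVA may be measured on any standard VA chart according to local clinical practice". Appendix 8 says that the ETDRS "chart is recommended, but Snellen and LogMAR are also acceptable". Within a patient the chart is fixed: Appendix 8 says the chart used for "VA on Day 1 must remain consistent for the duration" of participation, and Table 2 adds for an unscheduled visit that "the same method of VA assessment should be used as the baseline assessment".

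Table 2 schedules best-corrected visual acuity (BCVA) once, on Day 1. The scheduled check after injection is finger counting, which gives no chart score. Section 8.2.1 provides for further visits: "If warranted during the study duration (7 days), patients will be asked to return to the clinic as soon as possible". Appendix 9 makes acuity part of each one: BCVA, slitlamp, intraocular pressure and "indirect ophthalmoscopy examinations must be conducted at unscheduled safety visits".

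**The concern.** One criterion is written three ways, and the three do not agree at the limit. Because the chart follows local practice, two patients with the same loss can be classified differently only because their sites use different charts.

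The reference for the loss also moves. At a first unscheduled visit the preceding chart score is the Day 1 score. At a second it is the score from the first unscheduled visit, which may already be reduced. An eye that loses vision in steps can lose well over 30 letters without meeting the criterion.

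What is at stake is whether an event is labelled AESI and SAE, and whether it must be reported within 24 hours. Section 3 plans no patient-related safety endpoint, but adverse events, AESIs and SAEs are the patient safety data to be summarised, so consistent labelling has some value even in a small study.

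**Working it through.** **Inputs from the protocol.** Limits of ≥ 30 letters, > 0.6 logMAR and > 6 lines, and a reference equal to the assessment before the most recent one (Section 8.3.8). One scheduled BCVA, on Day 1 (Table 2). BCVA at every unscheduled visit, with no stated cap on the number of visits (Appendix 9).

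**Assumption.** 5 letters per line and 0.1 logMAR per line, hence 0.1 / 5 = 0.02 logMAR per letter. The protocol gives no conversion.

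**Step 1: are the three limits the same size?** 30 / 5 = 6 lines and 6 × 0.1 = 0.6 logMAR. The nominal values reproduce one another, so only the signs differ.

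**Step 2: apply the signs.**

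| Loss | ETDRS, ≥ 30 | LogMAR, > 0.6 | Snellen, > 6 lines |
|---|---|---|---|
| 29 letters = 0.58 = 5.8 lines | no | no | no |
| 30 letters = 0.60 = 6 lines | yes | no | no |
| 35 letters = 0.70 = 7 lines | yes | yes | yes |

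On a LogMAR chart scored by letter, 31 × 0.02 = 0.62 already qualifies, so the gap there is a single value.

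**Step 3: range of the assumption.** Keep 0.1 logMAR per line and vary the letters per line.

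- At 4 letters per line, 30 letters is 30 / 4 = 7.5 lines, or 0.75 logMAR.
- At 6 letters per line, 30 letters is 30 / 6 = 5 lines, or 0.5 logMAR.

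At either value the limits differ in size as well as in sign. The difference in sign is in the text whatever the conversion.

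**Step 4: the reference.** These are illustrative letter scores on Day 1, at a first unscheduled visit and at a second. Neither path meets the limit at the first visit (a loss of 20, and a gain of 12).

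| Path | Loss at second visit against preceding | Loss at second visit against Day 1 | Current rule | Day 1 only | Either reference |
|---|---|---|---|---|---|
| 75, 55, 35 | 20 | 40 | no | yes | yes |
| 60, 72, 42 | 30 | 18 | yes | no | yes |

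Under the current rule, two steps of up to 29 letters each, 29 + 29 = 58 in total where the starting score allows, would not meet the ETDRS limit. The second path shows that putting Day 1 in place of the preceding assessment would lose an acute fall that follows an interim gain.

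**The case against.** The practical reach is small. A charted acuity after injection exists only if a patient returns for an unscheduled visit within about 7 days. The difference in sign then matters only if that patient is on a chart other than the recommended ETDRS and has a loss at the limit. The moving reference matters only with a second such visit. The protocol gives no frequency for any of this. All of that stands.

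Other routes remain open for an event that misses this criterion. Intervention to prevent permanent loss of sight and severe intraocular inflammation qualify separately (Section 8.3.8). Important medical events should usually be considered serious (A2-2). A persistent event that becomes serious must be reported within 24 hours (A2-7.3). All adverse events are recorded to Day 7 (Section 8.3.1) and followed to resolution or stability (Section 8.3.3). This stands too, though the important-medical-event route rests on judgement and the other two sight-threatening routes on a different clinical picture. None of them makes the numerical limits agree.

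The preceding assessment is also a defensible reference, because it catches an acute fall after an interim gain. That stands, and it is a reason to keep it and add Day 1, not to exchange one for the other.

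A reader might go further and infer a wider mismatch from whole-line scoring or from unevenly spaced Snellen charts. The documents do not support this. They give neither a scoring rule nor chart geometry, and rounding to whole lines would remain largely untouched by a change of sign. A reader might also infer that a patient's classification could change through a switch of chart. Appendix 8 rules that out by fixing the chart for each patient.

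**Conclusion.** The point holds as a minor correction. The inclusive and strict signs in Section 8.3.8 conflict on the face of the text, and no other section harmonises them. With 5 letters and 0.1 logMAR per line assumed, a loss of exactly 30 letters, 0.6 or 6 lines is an AESI and SAE on ETDRS but not on the other charts, and the difference falls between patients or sites. Separately, from a second unscheduled visit a stepwise loss such as 20 + 20 letters does not meet the criterion, although it is 40 letters from Day 1.

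The effect is limited to AESI/SAE classification and expedited reporting, and I expect it to be rare among about 35 patients over 7 days. It would be too strong to conclude that such events go unrecorded or that the study's safety results are undermined. All adverse events are collected to Day 7, and no patient-related endpoint (Section 3) or hypothesis test (Section 9.1) depends on this criterion.

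**What to change.** In Section 8.3.8:

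- The sponsor should reconcile the three limits so that they carry the same inequality sign. The choice of sign is the sponsor's. An inclusive sign brings in losses exactly at the LogMAR and Snellen limits; a strict sign takes out a loss of exactly 30 ETDRS letters.
- Add the Day 1 pre-injection BCVA, on the same chart, as a reference beside the preceding assessment, so that a loss at the limit against either one qualifies. Do not drop the preceding assessment.

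The cost is a wording change. The Day 1 BCVA is already collected (Table 2) and the chart is already fixed within a patient, so no assessment is added. The downside is that a few more events may become reportable as AESIs and SAEs within 24 hours.
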